Three randomized controlled trials comparing nasojejunal and nasogastric feeding routes in patients with severe acute pancreatitis found no significant differences in terms of feeding tolerance, complication rates, or mortality [38-40]. Four meta-analyses [41-44] have concluded that nasogastric tube feeding is a feasible, safe, and well-tolerated approach in patients with severe acute pancreatitis. Compared to nasojejunal feeding, it does not lead to higher rates of complications, mortality, recurrence of refeeding pain, or extended hospital stay. Unfortunately, to date, there have been no published studies specifically addressing the topic of nutritional support in patients with pancreatic collections treated using minimally invasive approaches. In a large Dutch trial demonstrating the superiority of the endoscopic approach over the surgical step-up strategy [84], specific data on nutritional support were not reported. However, all patients were provided with oral nutrition when tolerated. In cases of oral intolerance, enteral nutrition was delivered via a nasojejunal feeding tube, and parenteral nutrition was administered when enteral nutrition was contraindicated [45].

Aims and Objectives:

Aim:

To compare outcomes of Nasojejunal feeding vs oral feeding following endoscopic transluminal drainage in patients with symptomatic walled-off necrosis

Primary Objectives:

1. To compare the rate of nutritional failure at Day 14 between Nasojejunal and oral feeding post endoscopic transmural drainage of WON.

Secondary Objectives:

1. To compare infection rates, need for antibiotic escalation and new onset organ failure
2. To compare re-intervention needs and hospital stay duration
3. To compare patient weight, serum albumin and inflammatory markers (CRP)
4. To compare GI complications (Vomiting, diarrhoea, aspiration pneumonia, feeding intolerance)
5. To compare patient reported outcomes (appetite, pain ,quality of life)

Materials and Methods:

Study design

The study will be a prospective, open label, single centre, randomized controlled trial. It will be conducted in the Department of Gastroenterology, PGIMER, from July 2025 to December 2026

Study Population:

All patients presented to PGIMER with WON due to acute pancreatitis requiring EUS guided transluminal drainage will be screened for inclusion criteria.

Inclusion criteria

1. Patients of acute pancreatitis (AP) with 18-75 years of age

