2. Patients with symptomatic WON requiring EUS guided transluminal drainage
3. Provision of written informed consent

Exclusion criteria

1. Patients with collection not amenable for EUS guided drainage (distance of WON >1 cm from the gastrointestinal lumen)
2. Known malignancy or immunocompromised state
3. Previous upper gastrointestinal(GI) surgery interfering with absorption
4. Active GI bleeding
5. GI obstruction, ileus or persistent vomiting
6. Patients moribund to undergo endoscopic procedure (Glasgow coma scale <8 or patients on ventilatory support)
7. Patients with irreversible coagulopathy like platelets <50,000/mm³ and/or INR>1.5
8. Pregnant or lactating female

WON: WON will be defined as a mature, encapsulated collection of pancreatic and/or peripancreatic necrosis that has developed a well-defined inflammatory wall. [3]

Symptomatic WON: It will be defined by any of the following: 1) Infected WON, or 2) Presence of pressure symptoms like abdominal pain, early satiety, weight loss or biliary duct compression or 3) persistent pain abdomen

Infected WON: It will be defined by any of the following: 1) As evident on by a positive Gram's stain or culture from a fine-needle aspiration or 2) the presence of gas configurations within collection on contrast-enhanced computed tomography (CT) or 3) clinical signs of infection; defined as persistent organ failure or persistence of two inflammatory variables (temperature $>38.5^{\circ}\text{C}$ or elevated C-reactive protein levels or leukocyte counts) during 3 consecutive days.

SIRS: Presence of ≥ 2 out of the following parameters: Temperature $< 36^{\circ}\text{C}$ or $>38^{\circ}\text{C}$, Total leukocyte count $< 4000/\text{mm}^3$ or $>12000/\text{mm}^3$, Respiratory rate $> 20/\text{min}$ or PaCO_2 of $< 32\text{mmHg}$, Heart rate $> 90/\text{minute}$ [41]

Organ failure- It will be defined as per modified Marshall criteria [4]

Technical success: Successful placement of metal stent with EUS guided transluminal drainage.

Clinical success: Post endoscopic treatment collection size ≤ 3 cm on any cross-sectional imaging before removal of metal stent along with resolution of initial symptoms requiring drainage.

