- Patient will be started on oral liquid then on soft diet. Escalation will be guided based on feed tolerance. Oral diet will be supplemented with parenteral nutrition if caloric intake is <60% of target calorie at Day 5.

Nutritional failure at Day 14:

Definition:

- <75% calorie requirements are met
- Need for parenteral nutrition
- Severe GI intolerance requiring feed modification

Infectious complications:

The patient should have signs of bacterial infections/fungal infections i.e. body temperature $>100^0$ F and raised leukocytes, CRP, Procalcitonin, beta-D glucan and galactomannan.

| Infection | Definition |
|-------------------------------------|---|
| Infected pancreatic necrosis | Positive culture after first percutaneous drainage procedure of collection with (peri-) pancreatic necrosis |
| Bacteremia | Positive blood culture Positive culture in 1 blood culture. In case of coagulase negative staphylococci or other non-virulent micro-organisms at least 2 blood culture bottles are mandatory. |
| Pneumonia | Coughing, dyspnoea, radiography with infiltrative abnormalities and positive culture in sputum. On the intensive care unit, a positive endotracheal culture is mandatory |
| Sepsis | SIRS and positive blood culture |
| | |

Statistical analysis:

All patients after randomization will be evaluated for primary and secondary endpoints. Data will be explored for any outliers, errors and missing values. When data will be normally distributed, continuous variables will be compared using Student's t-test. For skewed data, Mann-whitney test will be used. Quantitative data will be described as median with range and mean with standard deviation. Categorical data will be shown as proportions. Multiple linear regression analysis will be performed to identify risk factors for requirement of additional intervention after initial drainage procedure. 95% confidence interval will be taken as a cut-off for significance. Intention to treat and per-protocol analysis will be performed. The analysis was performed using Statistical Packages for the Social Sciences (SPSS Inc, Chicago, IL, version 22.0 for windows).

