|-------|------------|----------|------------------------------|--------------------------------|-----------------------|--------------|
| DEN 1 | | | | | | |
| DEN 2 | | | | | | |
| DEN 3 | | | | | | |

B. Metal Stent NJ feed:

Nutritional assessment:

| Date | Day 0 | Day 1 | Day 2 | Day 5 | Day 8 | Day 11 | Day 14 |
|-----------------|-------|-------|-------|-------|-------|--------|--------|
| Calorie intake | | | | | | | |
| Protein intake | | | | | | | |
| Change in route | | | | | | | |

| Weight | Day 0 | Day 14 |
|--------|-------|--------|
| | | |

| Date | Day 0 | Day 7 | Day 14 |
|---------------------------------|-------|-------|--------|
| Albumin | | | |
| CRP | | | |
| Total length of hospitalization | | | |

| Date | Adverse events related to feed |
|------|--------------------------------|
| | |
| | |
| | |
| | |
| | |
| | |
| | |

| Date | Indication | Stent migration/ Blockage | Stent removal/ PS placement | Complete necrosectomy | Complication |
|-------|------------|------------------------------|--------------------------------|-----------------------|--------------|
| DEN 1 | | | | | |
| DEN 2 | | | | | |
| DEN 3 | | | | | |

Parameters after Index Procedure:

| | | Day 0 | Day 3 | Day 7 | Day 14 | Day 21 | Day 28 |
|----------------|------|-------|-------|-------|--------|--------|--------|
| Fever | | | | | | | |
| SIRS | | | | | | | |
| OF | ALI | | | | | | |
| | AKI | | | | | | |
| | CVSF | | | | | | |
| Hemoglobin | | | | | | | |
| TLC | | | | | | | |
| CRP | | | | | | | |
| APACHE II | | | | | | | |
| BISAP | | | | | | | |
| Urea/Crt | | | | | | | |
| T. Bil/ D. Bil | | | | | | | |
| Albumin | | | | | | | |
| AST/ALT/ALP | | | | | | | |
| Procalcitonin | | | | | | | |
| Blood Culture | | | | | | | |
| NCD culture | | | | | | | |
| PCD culture | | | | | | | |

Fluid Analysis:

| | Total cells/ Differential cells | Glucose | Protein/ Albumin | Amylase/ Lipase | LDH | CA 19.9 | Culture |
|-----------------------|---------------------------------------|---------|---------------------|--------------------|-----|---------|---------|
| Ascitic fluid | | | | | | | |
| NCD / WON fluid | | | | | | | |
| PCD fluid | | | | | | | |

Antibiotics:

| No | Antibiotics/ Antifungal | Culture based (Y/N) | Duration | No | Antibiotics/ Antifungal | Culture based (Y/N) | Duration |
|----|----------------------------|---------------------------|----------|----|----------------------------|------------------------|----------|
| 1 | | | 4 | | | | |

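### As written, the general condition above the infection table asks for fever, three inflammatory markers and two fungal markers together for every infection type, and it contradicts the protocol's own sepsis and SIRS definitions

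*Protocol*

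**What the plan says.** The first secondary objective in the protocol's Aims and Objectives is "To compare infection rates, need for antibiotic escalation and new onset organ failure". The section Infectious complications defines what counts as an infection, in two layers.

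- **General condition.** A sentence above the table reads "The patient should have signs of bacterial infections/fungal infections i.e. body temperature" above 100 F, and continues with "raised leukocytes, CRP, Procalcitonin, beta-D glucan and galactomannan". The list is introduced as a definition, not as examples.
- **Table rows.** Infected pancreatic necrosis, bacteraemia, pneumonia and sepsis each have their own definition. All four rest on a positive culture. Pneumonia adds symptoms and radiography, and sepsis is "SIRS and positive blood culture".

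SIRS is defined after the exclusion criteria: "SIRS: Presence of ≥ 2 out of the following parameters". The four parameters are temperature below 36 °C or above 38 °C, leukocytes below 4000 or above 12000 per mm³, respiratory rate above 20 per minute or PaCO2 below 32 mmHg, and heart rate above 90 per minute.

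In the Thesis Proforma, the grid headed "Parameters after Index Procedure" covers Days 0, 3, 7, 14, 21 and 28. It lists fever, SIRS, leukocytes, CRP, procalcitonin and blood culture, but neither beta-D glucan nor galactomannan. Those two markers, with procalcitonin, stand in a separate small table after the baseline laboratory reports. That table has a date row and blank columns.

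**The concern.** The sentence sits above the whole table, so it reads as an entry condition for every row. Taken that way, it asks for two fungal markers before a bacterial infection can be counted. It also asks for fever and raised leukocytes in a section whose Sepsis row accepts their opposites.

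The trial is open label with 20 patients per arm, so infections will be few and moving one or two of them changes the comparison. If the rule is followed, culture-proven events are dropped. If it is not followed, the assessor decides case by case which signs to waive, knowing the feeding route. The first course loses information, and the second opens a path to bias.

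**Working it through.** **1. Is the condition conjunctive as written?** It lists six signs: temperature, leukocytes, CRP, procalcitonin, beta-D glucan and galactomannan. They are joined by 'and', with no 'or' and no minimum number. Elsewhere the protocol marks alternatives when it means them. The infected-collection definition begins "Infected WON: It will be defined by any of the following", and SIRS needs two of four parameters. The plain reading is therefore that all six are required.

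**2. Condition against the Sepsis row.** Take a patient with a positive blood culture.

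| Route to SIRS (two or more of four) | Sepsis row | General condition |
|---|---|---|
| Temperature <36 °C plus another parameter | met | fails on temperature, unless fever is also recorded |
| Leukocytes <4000 plus another parameter | met | fails on leukocytes |
| Heart rate >90 and respiratory rate >20 only | met | fails on temperature or leukocytes if either is normal |

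The temperature limits differ too. (100 − 32) × 5/9 = 37.8 °C for the general condition, against above 38 °C (100.4 °F) or below 36 °C (96.8 °F) for SIRS. The two statements cannot both govern the same event. This step needs no outside figure.

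**3. Condition against the Bacteraemia and Pneumonia rows.** Both rows can be met in full by a bacterial infection. The general condition then rejects the event unless both fungal markers are also raised.

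**4. Size.** The plan gives no infection rate and no marker frequency, so there is no figure to reproduce. The following is illustration under stated assumptions only: 20 per arm, a true infection rate of 20–40% (4–8 infections per arm), and independent signs.

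Counted infections = true infections × share meeting the rule.

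| Assumption | Share kept | Counted per arm |
|---|---|---|
| Four non-fungal signs each 80%, fungal pair 10% | 0.8⁴ × 0.10 = 0.041 | 0.2–0.3 |
| Four non-fungal signs each 90%, fungal pair 30% | 0.9⁴ × 0.30 = 0.197 | 0.8–1.6 |
| All six signs each 90% | 0.9⁶ = 0.531 | 2.1–4.3 |
| Fungal pair dropped, other four still all required, 80–90% each | 0.410–0.656 | 1.6–5.2 |

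The last row shows that removing the fungal markers alone is not enough. Requiring the other four jointly still discards a third or more of infections under these assumptions.

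**5. Effect on the comparison.** If the rule loses the same share in both arms, the ratio of rates is preserved but the difference shrinks. For example, assumed rates of 40% and 20% at a share kept of 0.197 become 7.9% and 3.9%. A 20-point difference becomes about 4 points.

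**6. Data capture.** Leukocytes, CRP, procalcitonin and blood culture have scheduled entries to Day 28. The two fungal markers have none. They can be entered in the separate table, but nothing ties an entry there to an infection.

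**The case against.** The strongest reply is that the sentence is a pooled list. It speaks of bacterial and fungal infections with a slash and then names markers of both kinds, so the authors may have meant each marker for its own kind of infection. Each row also carries its own culture-based definition. This is plausible as intent. The text does not say it, however, and an assessor has no instruction on which signs may be left out. The objection is a reason to rewrite the sentence.

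Three stronger readings are tempting, and the documents do not support them.

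- **Bacterial infections cannot count at all.** They count if both fungal markers happen to be raised along with the other signs. The exclusion is certain only where a required sign is absent.
- **The infection rate will be close to zero, with most events lost.** That depends on a marker frequency that the documents do not give. The background reports fungi in 22% of index endoscopy samples, which is not a marker frequency but shows that fungal involvement is not negligible.
- **The fungal markers cannot be recorded at an event.** The proforma table has a date row with blank columns, so they can be. They are merely unscheduled.

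It is also fair that infection is one secondary outcome in a pilot sized for feasibility, that literal under-counting would affect both arms, and that most of the needed data are collected. These points lower the severity. They do not remove the contradiction with the Sepsis row.

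**Conclusion.** The point stands as a defect in a stated definition. As written, the general condition excludes culture-proven bacterial events without both fungal markers raised, and it contradicts the Sepsis row and the SIRS definition behind it. The contradiction follows from the text alone.

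The direction is under-counting under literal use, or unblinded discretion under loose use. The size is unknown: the 4–53% range of infections kept rests entirely on assumed sign frequencies, independence and an assumed true rate. The sentence should be corrected before infections are classified. The outcome is secondary, so this does not threaten the primary comparison of nutritional failure.

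**What to change.** Replace the general sentence along these lines:

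- Each row's own criteria (culture, and for pneumonia symptoms and radiography) define the event. Any supporting signs are stated as alternatives.
- Beta-D glucan and galactomannan are not required for bacterial events and serve only to support a fungal infection.
- Sepsis rests on the protocol's SIRS definition and a positive blood culture, with no further fever or leukocytosis condition.
- Bacteraemia stays as a positive culture under its own row. Adding SIRS to it would make it largely the same as Sepsis.

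The cost is one rewritten paragraph. No new tests are needed, because leukocytes, CRP, procalcitonin and blood cultures are already in the follow-up grid. The downside is slightly lower specificity than the literal rule.

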Randomization: Patients needing EUS guided drainage with LAMS for symptomatic WON will be randomized once they fulfil inclusion criteria. Computer generated randomization assignments will be provided in advance using block randomisation and placed in sequentially numbered sealed envelopes. They will be opened during the procedure to determine treatment allocation.

Study flow:

Patients of AP with infected WON who are planned for EUS guided transluminal drainage by LAMS will be screened for inclusion criteria. Patients who fulfilled inclusion criteria will be randomized into either Nasojejunal (NJ) feeding or oral feeding after informed consent.

[figure not shown]
Sample size:

Since it is a pilot study and in a year the unit treats approximately 80-100 patients with WON and therefore considering exclusions a feasibility sample size of 20 in each arm will be taken.

Techniques:

Initial diagnostic EUS:

EUS examination will be done under conscious sedation using intravenous midazolam. Linear scanning echoendoscope (EG-3870 UTK linear echoendoscope, Pentax Inc., Tokyo, Japan or

UCT180 linear echoendoscope, Olympus Optical Co Ltd, Tokyo, Japan) will be used at a frequency of 7.5 MHz. The WON and surrounding areas will be first carefully scanned on EUS with special emphasis on size as well as detailed morphology of WON. Colour Doppler will be used to detect any intervening vascular collaterals.

Quantification of solid necrotic debris on EUS:

The echogenic material present in the WON is suggestive of solid necrotic debris. An attempt to quantify the amount of solid debris as percentage of total size of collection will be done. The quantification of the solid debris will be an approximate visual judgment of the endoscopist.

Randomization:**A. Nasojejunal (NJ) feeding group:**

- Patients randomized to this group will have NJ placement within 24 hours post-drainage.
- NJ will be placed endoscopically
- NJ position will be confirmed by Abdominal X-ray (AXR)
- Standard formula feed will be initiated immediately after placing and confirming the NJ position with a rate of
 - First 24 hours : 25 ml/hr
 - Between 24-48 hours : 50 ml/hr
 - Between 48-72 hours: increase to full nutrition
 - After 72 hours: Full nutrition
- Full nutrition is defined as an energy target of 30kcal/kg/day

.

B. Oral feeding group:

- Patients randomized to this group will initiated on oral feed post procedure as tolerated.

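### The infected pancreatic necrosis outcome requires a percutaneous drain although every patient is drained under EUS, and it does not set apart infection already present at entry

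*Protocol*

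**What the plan says.** Under Infectious complications, the protocol first asks for general signs of infection (fever and raised laboratory markers) and then defines four infection types in a table. The row for infected pancreatic necrosis reads "Positive culture after first percutaneous drainage procedure of collection with (peri-) pancreatic necrosis". The other rows are bacteremia, pneumonia and sepsis. Comparing infection rates is part of the first secondary objective, and the Study design paragraph states that the trial is open label.

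The population is drained by another route. Inclusion criterion 2 admits "Patients with symptomatic WON requiring EUS guided transluminal drainage", and collections that EUS cannot reach are excluded. The Randomization paragraph says "Patients needing EUS guided drainage with LAMS for symptomatic WON will be randomized". Percutaneous drainage of participants appears only in the Thesis Proforma, as a yes/no item near the end and as a place to record its cultures and fluid results.

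Infection can be present at entry. Of symptomatic WON the protocol says "It will be defined by any of the following: 1) Infected WON", followed by pressure symptoms and persistent pain as alternatives.

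**The concern.** The specimen named in the outcome definition does not fit the procedure that the trial performs. A definition tied to the percutaneous route leaves out infected collections handled entirely by endoscopy, which is the pathway the trial is built around. It also makes the outcome depend on a treatment step. Where a percutaneous drain is placed after allocation, that decision is made with the arm known, so a difference between arms on this row could reflect drain use rather than infection.

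Nothing in the row or its lead-in requires the infection to be new. In the first secondary objective, the new-onset qualifier is attached to organ failure and not to infection. Infection that brought the patient into the trial could therefore be counted as if it had followed the feeding strategy.

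**Working it through.** The protocol attaches no rate, power or sample-size figure to this outcome, so there is nothing to reproduce. The check sets the sections side by side.

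| Element | Where | Content |
|---|---|---|
| Specimen for the outcome | Infectious complications, table | Culture after the first percutaneous drainage |
| Index procedure | Inclusion criteria; Randomization | EUS-guided transluminal drainage for all |
| Percutaneous catheter | Thesis Proforma, near the end | Yes/no, no date of placement |
| Cultures collected | Parameters after Index Procedure; Fluid Analysis | NCD, PCD (percutaneous drain) and blood cultures on Days 0, 3, 7, 14, 21 and 28; NCD/WON and PCD fluid cultures, undated |
| Infection at entry | Infected WON definition; Indication of Drainage | FNA stain or culture, gas on CT, or clinical signs; recorded as the drainage indication |

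**Literal reading.** Only patients with a percutaneous drain can meet the row. With 20 per arm there are 40 patients, so if a share r has such a drain, at most 40 × r can be counted. The protocol does not give r. Purely as assumptions:

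- r = 10%: 40 × 0.10 = 4 can meet the row, 36 cannot.
- r = 25%: 40 × 0.25 = 10 can, 30 cannot.
- r = 50%: 40 × 0.50 = 20 can, 20 cannot.

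Those who cannot are excluded whatever their NCD or WON-fluid culture shows. A patient may thus satisfy the entry definition of infected WON and still be unable to satisfy the outcome row.

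**Reading percutaneous as a slip.** The row becomes a positive culture after the first drainage. That takes in later cultures from the serial table, and it does not rule out a culture that reflects infection at entry. Let b be the share in each arm counted because of infection at entry (equal in expectation under randomisation), and p1 and p2 the rates of later infection among the rest. The rate in arm i is b + (1 − b) × p_i, so the difference between arms is (1 − b) × (p1 − p2). For b between 0 and 1 this is smaller than p1 − p2. The protocol gives none of b, p1 and p2, so only the direction can be stated. The lead-in signs must also be met, so b need not equal the share with infected WON at entry.

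**Which sample is baseline.** Of the allocation envelopes the protocol says "They will be opened during the procedure to determine treatment allocation". Feeding starts afterwards: "Patients randomized to this group will have NJ placement within 24 hours post-drainage" in one arm, and "Patients randomized to this group will initiated on oral feed post procedure as tolerated" in the other. A sample taken at the index drainage therefore precedes the allocated feeding and describes the patient at entry.

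**Scope.** Bacteremia and sepsis rest on blood culture, and pneumonia on symptoms, radiography and a respiratory culture. Nutritional failure at Day 14 uses no culture. None of these depends on the drainage route.

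**The case against.** The strongest defence is that only one word is wrong. The row sits under complications, it also needs the clinical signs in the lead-in, and infection at entry has its own definition and is recorded as the drainage indication. How baseline infection enters the analysis may reasonably be left to a statistical analysis plan, which is not at hand. Much of this stands: a positive entry culture alone does not meet the row, and the data for separating old from new infection largely exist. But the specimen route is fixed in the protocol, no other section corrects it, and no section links the recorded entry status to the outcome.

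It is also fair that drain use after randomisation is partly inferred. The form gives no date of placement, and the exclusion criteria do not rule out an earlier percutaneous drain.

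Two stronger readings are tempting and should not be adopted.

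- A reader might infer that, with percutaneous taken as a slip, the outcome is the index-procedure culture, so that feeding could not affect it and the expected difference is zero. The row says after the drainage, not at it, and the form schedules cultures to Day 28.
- A reader might infer that all patients are infected at entry, because Study flow says "Patients of AP with infected WON who are planned for EUS guided transluminal drainage by LAMS will be screened for inclusion criteria". That sentence describes screening. The aim, inclusion criterion 2 and the Randomization paragraph all say symptomatic, and the form lists non-infective indications for drainage.

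**Conclusion.** Wrong as written. Followed literally, the row cannot register infected necrosis in patients managed by EUS alone, and it partly tracks who received a percutaneous drain. With the word percutaneous set aside, it still mixes infection at entry with later infection, which would pull any difference between arms towards zero.

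Neither effect can be sized from the documents. The counts of 4 to 20 patients able to meet the row rest on assumed drain rates, and the dilution is given in direction only, assuming equal entry infection in the two arms. The consequence is limited to one of four infection types under a secondary objective, in a pilot of 40 patients that makes no power claim. The primary endpoint and the bacteremia, pneumonia and sepsis rows are unaffected.

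**What to change.** Reword the row as a positive culture of collection fluid by any route (EUS aspirate, NCD or PCD), together with the clinical signs that the lead-in already requires. Add one sentence making the index-procedure (Day 0) culture and the recorded drainage indication the baseline infection status. Count only later positive cultures that meet the definition as post-randomisation events.

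The cost is one reworded row, one sentence, and a sample-date field in the Fluid Analysis table, which has none. The serial table already places NCD, PCD and blood cultures by day, and the drainage indication is already on the form. The change concerns outcome classification only and asks for no change in patient care.

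Three downsides should be stated as limitations:

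- There will be fewer countable events, because entry infections no longer count.
- Cultures taken once a transluminal stent is in place may show colonisation from the gut, possibly to a different degree under oral and jejunal feeding. Requiring clinical signs reduces this but does not remove it.
- Later samples will come mainly from patients with a drain or a repeat procedure, so ascertainment still depends partly on the clinical course.

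### The sepsis definition lacks the two-bottle rule that the bacteraemia definition applies to low-virulence organisms, so the graver label has the weaker culture standard

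*Protocol*

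**What the plan says.** The protocol defines its infections in a short table under Infectious complications. A sentence above the table sets a condition for all rows. It begins "The patient should have signs of bacterial infections/fungal infections i.e. body temperature" and goes on to a temperature threshold of 100 °F and raised leukocytes, CRP, procalcitonin, beta-D glucan and galactomannan.

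The bacteraemia row has two tiers. The general rule is "Positive culture in 1 blood culture". For organisms that are often contaminants it is stricter: "In case of coagulase negative staphylococci or other non-virulent micro-organisms at least 2 blood culture bottles are mandatory".

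Two rows further down, sepsis is defined in full as "SIRS and positive blood culture". SIRS is defined earlier in Materials and Methods, after the exclusion criteria, as "Presence of ≥ 2 out of the following parameters", the four parameters being temperature, leukocyte count, respiratory rate or PaCO2, and heart rate. That definition says nothing about cultures.

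The table serves the first secondary objective: "To compare infection rates, need for antibiotic escalation and new onset organ failure". The data form (Parameters after Index Procedure) has a row "Blood Culture" beside rows for fever and SIRS, with columns for Days 0, 3, 7, 14, 21 and 28. In the readable text that row has one cell per day and no separate place for the organism or the number of positive bottles.

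**The concern.** The two rows rest on the same laboratory test but, as worded, do not use it in the same way. The bacteraemia row guards against a single contaminated bottle; the sepsis row does not. One would expect sepsis, as defined here, to be the more severe part of bacteraemia: the same blood culture finding plus a systemic response. On the literal wording it is not, because a patient can enter the sepsis count without qualifying for the bacteraemia count.

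At stake is the reliability of one component of the infection comparison. Two assessors could classify the same patient differently, depending on whether they carry the bottle rule down from one row to the other. With 20 patients per arm, a single such classification is visible in the reported proportion.

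**Working it through.** The protocol states no figure on this point, so there is nothing to reproduce. The check compares the two definitions over all relevant combinations.

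**Inputs, all from the protocol**

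- L: the general signs of infection above the table are met (yes/no). They apply to every row.
- S: SIRS is present, at least 2 of 4 parameters (yes/no).
- b: number of bottles growing a low-virulence organism (1 or 2).
- Arm size: 20 (Sample size).

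**Rules for a low-virulence organism**

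- Bacteraemia = L and b ≥ 2.
- Sepsis as worded = L and S and b ≥ 1.
- Sepsis if it used the bacteraemia culture rule = L and S and b ≥ 2.

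| L | S | b | Bacteraemia | Sepsis as worded | Sepsis with the bottle rule |
|---|---|---|---|---|---|
| no | no | 1 | no | no | no |
| no | no | 2 | no | no | no |
| no | yes | 1 | no | no | no |
| no | yes | 2 | no | no | no |
| yes | no | 1 | no | no | no |
| yes | no | 2 | yes | no | no |
| **yes** | **yes** | **1** | **no** | **yes** | **no** |
| yes | yes | 2 | yes | yes | yes |

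One of the eight combinations is inconsistent: general signs met, SIRS present, one bottle. Only this cell changes when the bottle rule is carried into the sepsis row.

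**Other organisms.** One positive culture satisfies both rows, so sepsis is already bacteraemia plus SIRS and nothing is inconsistent.

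**Role of the general signs.** Rows three and four of the table show that SIRS with a positive culture is not sepsis when the general signs are absent. The condition therefore limits how often the problem can arise. It does not remove it, because it applies equally to both rows and so cannot restore a bottle rule that one of them lacks.

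**Scale.** One patient in an arm of 20 is 1/20 = 5 percentage points. How many patients would fall in the inconsistent cell depends on the contamination rate per culture, the number of cultures actually taken, and how often SIRS and the general signs are present at the time. The protocol gives none of these, so no expected count is derived.

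**The case against.** The best case for the protocol is that the bacteraemia row is itself the definition of a positive blood culture. It opens with that term and then says what qualifies; the sepsis row uses the same term two rows later. On that reading the bottle rule carries over and there is no mismatch. This reading is available, and the repetition at the start of the bacteraemia row may be no more than table cells merged when the PDF was read. But nothing in the table says that the term carries over, and the sepsis row has no cross-reference. If it is what was meant, the proposed wording only makes it explicit.

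A second argument is that the general signs above the table are demanding, especially if beta-D glucan and galactomannan must both be raised, so that few contaminated cultures would ever reach the sepsis row. This stands as a limit on frequency. It also means that SIRS plus one contaminated bottle is not enough on its own to make sepsis under this protocol.

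Three stronger readings are tempting, and the documents support none of them:

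- **A number of false sepsis cases per arm.** A reader might multiply an assumed contamination rate by the day columns of the form and an assumed frequency of SIRS. Those rates are not in the protocol. Nor is the form a sampling schedule: the same grid has rows for drain cultures, including percutaneous drains, although the form treats a percutaneous drain as a yes/no contingency.
- **Bias between the arms.** A reader might infer that the oral arm, which has a written rule for adding parenteral nutrition, would have more lines, more cultures and more contamination. The readable text does not mention central lines and does not say that the arms will be cultured differently.
- **Double counting.** A reader might infer that sepsis and bacteraemia are added together. The protocol does not say so. A nested definition is ordinary, and how the components are combined per patient can properly be left to a statistical analysis plan.

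**Conclusion.** The point holds as an inconsistency of wording. As written, the sepsis row has a weaker culture standard than the bacteraemia row, and one identifiable type of patient is classed as septic without being bacteraemic: general signs of infection met, SIRS present, a single bottle growing a low-virulence organism. The conclusion rests on reading each row by its own words; if the bacteraemia row is taken to define the term for the whole table, the classification is consistent but the text leaves this unsaid.

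It is a minor matter. It touches one component of a secondary endpoint in a pilot trial and has no bearing on nutritional failure at Day 14 or on the sample size. Its frequency cannot be estimated from the documents; the only firm measure of scale is that each affected patient moves an arm's sepsis proportion by 5 percentage points. The infection definitions are fixed in the protocol's own table, so correcting them there does not anticipate what a separate analysis plan might cover.

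**What to change.** Change the sepsis row to *SIRS and bacteraemia as defined above*. The two-bottle rule then applies to both rows, and sepsis becomes a subset of bacteraemia under either reading of the present text.

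The cost is one line in the definition table. The downside is that a few doubtful single-bottle positives, some of which may be true infections, would no longer count as sepsis; the protocol already accepts that trade-off for bacteraemia. For the rule to be applied from the data form, the blood culture entry should also record the organism and the number of positive bottles, which adds two short fields.
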